12. EFFICACY PARAMETERS

Hypothesis testing of the primary efficacy endpoint will only be conducted if noninferiority could be established for the primary safety endpoint. The analysis of the primary efficacy endpoint will be carried out on both the FAS and PPS. The analysis using the PPS will be used as a supportive analysis.

12.1 Primary Analysis

For the primary efficacy endpoint of RR of λ FLC after 24 weeks of treatment, let μ_T denote the Theranova 400 dialyzer RR of λ FLC mean at 24 weeks and let μ_R denote the Elisio-17H dialyzer RR of λ FLC mean at 24 weeks. Then the null hypothesis to demonstrate superiority can be expressed as:

Ho: μ_T - $\mu_R = 0$. The alternative hypothesis is expressed as Ha: μ_T - $\mu_R \neq 0$.

The primary safety analysis will be conducted first. If the primary safety analysis demonstrates non-inferiority, an ANCOVA model with fixed effects of treatment and site will be used to generate a two-sided 95% CI for the difference in treatment means (μ_T - μ_R). If the lower bound is > 0 then superiority will be demonstrated. The statistical testing of the primary efficacy endpoint of the reduction ratio (RR) of λ FLC after 24 weeks of

treatment is contingent upon the outcome of the analysis of the primary safety endpoint and will only be conducted once non-inferiority could be established for the primary safety endpoint. This hierarchical testing approach guarantees that the overall Type I error is controlled at a two-sided 0.05 significance level.

The primary efficacy analyses will be performed using a multiple imputation approach. Multiple imputations using SAS Proc MI will be used to impute missing data under the missing at random assumption and the data sets generated will be analyzed using SAS Proc MIANALYZE (for more detail on missing data imputation see Section 7.2.2).

Twenty (20) complete data sets will be analyzed for the multiple imputation of the primary endpoint data.

12.2 Sensitivity Analysis

The impact of missing data on the primary efficacy analyses will be further explored as sensitivity analyses using observed data as well as last observation carried forward.

12.3 Secondary Analysis

The analysis of the secondary efficacy endpoints will be carried out on the FA.

In order to account for multiplicity, secondary efficacy analyses will be held to a hierarchical assessment and performed in the order outlined below. If the first analysis results in a p-value <0.05, then formal testing will continue to the second analysis. If the second analysis also results in a p-value <0.05, then formal testing will continue to the third analysis, and so on. This method of hierarchical assessment will continue until an analysis results in a p-value > 0.05, i.e., is considered statistically insignificant. This hierarchical approach guarantees that the overall alpha will not exceed 0.05.

- 1. MMRM of reduction ratio of λ FLC
- 2. MMRM of reduction ratio of CFD
- 3. MMRM of reduction ratio of κ FLC
- 4. MMRM of reduction ratio of IL-6
- 5. MMRM of reduction ratio of TNFα
- 6. MMRM of reduction ratio of β 2-microglobulin
- 7. ANCOVA of change in pre-dialysis β 2-microglobulin from baseline to 24 weeks
- 8. MMRM of Kt/Vurea

An MMRM model will be used to evaluate differences between treatment groups in the reduction ratios of λ FLC, CFD, κ FLC, IL-6, TNF α , β_2 -microglobulin after 4 weeks and after 24 weeks of treatment. The model will include the fixed effect of treatment, visit, and the random effect of patient.

An ANCOVA with a fixed effect of treatment and a fixed continuous effect of baseline pre-dialysis β_2 -microglobulin will be used to evaluate differences between treatment groups for the change from baseline in pre-dialysis β_2 -microglobulin after 24 weeks of treatment.

An MMRM model will be used to evaluate differences between treatment groups in Kt/V_{urea} collected after each 4 weeks of treatment. The model will include the fixed effect of treatment, visit, and the random effect of patient.

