5.3 Sample Size

The sample size for this study is driven by the primary safety endpoint. The sample size calculation was performed using PASS® 15.0.1 software, procedure Non-Inferiority Tests for the difference between Two Means. Copyright© 2017, NCSS, LLC. All Rights Reserved. The power is based on a t-test with a one-sided alpha level of 0.025 where the true difference in means is assumed to be zero (0) and the non-inferiority margin is 5%.

Pre-dialysis serum albumin was not evaluated in the previous Theranova 400 dialyzer HD study, only the mass (G) of albumin in the dialysate was assessed. However, a study published in PLoS ONE⁶ did use a prototype of the Theranova dialyzer (MCO-CI) where in pre-dialysis albumin levels were collected after a month of therapy and, based on these data, a mean and standard deviation (SD) of 35.3 and 3.7 was observed. Comparable pre-dialysis albumin levels are expected with both study dialyzers and with a sample size of 70 patients per group, a t-test with a 0.025 one-sided significance level will have 80% power to demonstrate non-inferiority of the Theranova 400 dialyzer compared to the Elisio-17H dialyzer as assessed by pre-dialysis serum albumin with a non-inferiority margin of 5%. To allow for 15% of patients to drop out, a total of 166 patients will be randomized 1:1 to treatment with the Theranova 400 dialyzer or treatment with the Elisio-17H dialyzer (i.e., 83 patients per group).

A previously conducted Theranova 400 dialyzer prototype HDF study (Comparison of the Clinical Performance of Two Theranova 400 Dialyzer Prototypes in Hemodialysis Mode with the Performance of a High-Flux Dialyzer in Hemodialysis Mode and a High-Flux Dialyzer in High-volume Hemodiafiltration Mode – A Pilot Study, registered at clinicaltrials.gov, NCT02377622) was used to obtain λ FLC reduction ratio mean and standard deviation (SD) of 37.8 and 8.26. With a total sample size of 140 evaluable subjects as determined based on the primary safety endpoint (70 in the Theranova 400 dialyzer treatment group and 70 in the Elisio-17H dialyzer treatment group), a difference of 4.56 in the λ FLC reduction ratio in favor of the Theranova 400 dialyzer can be detected with 90% power at a two-sided 0.05 significance level using a two-sided two-sample t-test assuming equal variances. Including 15% drop out, a total sample size of 166 (83 per treatment group) need to be enrolled into this study.

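### The secondary efficacy hierarchy has no entry condition from the two primary tests, so a formal λ FLC claim can follow a failed primary and each 0.05 guarantee holds only within its own family

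*SAP*

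**What the plan says.** One link between tests is written down. SAP 12 states: "Hypothesis testing of the primary efficacy endpoint will only be conducted if noninferiority could be established for the primary safety endpoint". SAP 12.1 then gives the success rule, "If the lower bound is > 0 then superiority will be demonstrated", and the claim for the primary pair: "This hierarchical testing approach guarantees that the overall Type I error is controlled at a two-sided 0.05 significance level". Protocol 10.5.2 and the synopsis say the same. Protocol 10.5 and SAP 11 describe this ordering as one for the primary endpoints.

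The secondary hierarchy is introduced in SAP 12.3 with "In order to account for multiplicity, secondary efficacy analyses will be held to a hierarchical assessment and performed in the order outlined below". Its movement rule is "If the first analysis results in a p-value <0.05, then formal testing will continue to the second analysis", and so on down eight steps. Step 1 is the λ FLC reduction ratio by MMRM, followed by CFD, κ FLC, IL-6, TNFα, β2-microglobulin (reduction ratio, then change in pre-dialysis level) and Kt/V. The reduction ratios are modelled "after 4 weeks and after 24 weeks of treatment. The model will include the fixed effect of treatment, visit, and the random effect of patient". The section closes its multiplicity paragraph with "This hierarchical approach guarantees that the overall alpha will not exceed 0.05". Protocol 10.6.2 and the synopsis carry the same rule. None of the three says what must have succeeded before step 1 is tested, and the SAP's list of changes from the protocol (SAP 10) adds no such condition.

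**The concern.** The plan puts safety first: if albumin non-inferiority is not shown, the primary λ FLC test is not done. Two sections later, formal testing of λ FLC is available again at two-sided 0.05, and a significant result opens the other solutes. An analyst who follows the text literally would report formal secondary significance in a trial that had failed its safety primary, its efficacy primary, or both.

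Two things are at stake. One is the status of the secondary claims after a failed primary. The other is the error statement: the primary pair and the secondary sequence each carry a 0.05 guarantee, and no rule joins them, so the two do not hold together across the trial. The primary decision rules, the sample size and the patients are not affected.

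**Working it through.** **Inputs from the documents** (SAP 5.3, 11.1, 12.1, 12.3): 70 evaluable per arm; albumin SD 3.7, margin 5% of 35.3, true difference 0, one-sided alpha 0.025, 80% power; λ FLC reduction ratio SD 8.26, difference 4.56, two-sided alpha 0.05, 90% power.

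**Assumptions not in the documents:** correlation *r* between the albumin and step-1 statistics; correlation *ρ* between week-4 and week-24 reduction ratios; correlation *k* between baseline and week-24 albumin. Step 1 is taken as one treatment effect averaged over weeks 4 and 24, because the model lists treatment and visit without an interaction.

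**1. The plan's own figures reproduce.**
- Margin: 0.05 × 35.3 = 1.765. Standard error: 3.7 × √(2/70) = 0.625. Non-centrality: 1.765/0.625 = 2.82. Power from the non-central t on 138 df: 0.800.
- λ FLC: 8.26 × √(2/70) = 1.396; 4.56/1.396 = 3.27; power 0.900.
- A fixed sequence with each step at 0.05 has family-wise error of at most 0.05, so the SAP 12.3 guarantee is right for its eight steps alone.

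**2. Albumin truly at the margin, step 1 null.** As written, error = P(Z_alb > 1.96 or |Z_1| > 1.96).
- Independent: 1 − 0.975 × 0.95 = 0.0738. For |r| = 0.3, 0.5, 0.7: 0.0726, 0.0704, 0.0667.
- Favouring Theranova only, P(Z_alb > 1.96 or Z_1 > 1.96): independent, 1 − 0.975² = 0.0494; 0.0500 at r = −0.7 and 0.0417 at r = 0.7.
- If step 1 required both primaries to succeed, any later error would need the albumin error first: 0.025.

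**3. Non-inferiority passed 80% of the time, λ FLC null at both visits.** The week-24 statistic and the two-visit average correlate at √((1+ρ)/2) = 0.806, 0.866, 0.922 for ρ = 0.3, 0.5, 0.7. The primary counts as a rejection only if its lower bound is above 0.
- Any direction: P(Z_24 > 1.96 or |Z_1| > 1.96) = 0.0638, 0.0617, 0.0590. Then 0.8 × that + 0.2 × 0.05 = 0.0611, 0.0593, 0.0572.
- Favourable only: 0.0388, 0.0367, 0.0340. Then 0.8 × that + 0.2 × 0.025 = 0.0361, 0.0343, 0.0322.
- With the entry condition: 0.8 × 0.025 = 0.020.

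**4. Both primary nulls false.** No primary false rejection is possible and the secondary sequence keeps its own 0.05. There is no inflation.

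**5. Claim status at the planning effects** (albumin difference 0, λ FLC difference 4.56 at both visits, tests taken as independent). Step-1 power with SD 8.26 × √((1+ρ)/2) is 0.980, 0.963, 0.940 for ρ = 0.3, 0.5, 0.7. The primary albumin analysis adjusts for baseline, so the residual SD is 3.7 × √(1−k²) (site degrees of freedom ignored):

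| k | Residual SD | Non-inferiority fails | Fails and step 1 significant (ρ 0.7 to 0.3) |
|---|---|---|---|
| 0 | 3.70 | 20.0% | 18.8–19.6% |
| 0.3 | 3.53 | 16.4% | 15.4–16.1% |
| 0.5 | 3.20 | 10.1% | 9.5–9.9% |
| 0.6 | 2.96 | 6.1% | 5.8–6.0% |
| 0.7 | 2.64 | 2.5% | 2.3–2.4% |

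With the entry condition this outcome cannot occur.

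**The case against.** The strongest reply is that the quoted sentence is not false where it stands. It follows the eight steps, is correct for them, and the word overall may even signal that a condition on the primaries was intended. That stands as far as it goes: a reader might infer that the secondary hierarchy itself fails to control its error, and it does not fail. But intention is not a rule. The same SAP writes out the safety-to-efficacy condition in both 12 and 12.1, so silence in 12.3 cannot be taken as a condition.

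Second, whether 0.05 is exceeded depends on which errors are counted. The any-direction figures include step-1 rejections against Theranova. Counting favourable errors only, neither scenario exceeds 0.05. This also stands; the fair comparison is then with the 2.0–2.5% that an entry condition would give. The first scenario, albumin exactly at the margin with no λ FLC effect, is a formal worst case and not a likely state for a larger-pore membrane.

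Third, a reader might infer that step 1 simply retests the hypothesis that was barred. It does not: the primary is an ANCOVA at week 24 and step 1 is an MMRM over visits. They share week-24 data under the visit list in SAP 12.3, but not under SAP 5.7, which lists the first day and week 4 for the secondary λ FLC endpoint. That difference needs its own reconciliation. Scenario 3 in the working uses the 12.3 list; the entry condition is missing under either.

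**Conclusion.** The point holds as a gap in the testing rules that should be closed. Nothing in either document conditions the secondary hierarchy on the primary tests, so the two 0.05 guarantees do not hold jointly. The cost in error is moderate: 6.7–7.4% in any direction (|r| 0.7 to 0) or 4.2–5.0% favourable (r 0.7 to −0.7), against 2.5%, with albumin at the margin; and 5.7–6.1% or 3.2–3.6% (ρ 0.7 to 0.3), against 2.0%, with λ FLC null.

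The 2–20% for a formal λ FLC claim after failed non-inferiority describes claim status. A reader might take it as a false-positive rate, but in that calculation the λ FLC effect is real. Its upper end assumes that baseline albumin explains nothing, although the planned ANCOVA adjusts for it. Much larger frequencies can be produced by supposing that Theranova truly lowers albumin; the plan assumes a zero difference, and those outcomes would not be errors either.

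**What to change.** Add to SAP 12.3, before database lock: *Formal secondary efficacy testing starts only if both the primary safety and primary efficacy tests succeed; otherwise secondary results are descriptive.* The sequence is then albumin, primary λ FLC, steps 1 to 8, and the trial-wide error is at most 0.05.

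If no such condition is intended, replace the guarantee with: *The type I error within the secondary efficacy family will not exceed 0.05; this does not cover the primary endpoints.*

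The first option costs any formal secondary claim when either primary fails. The second leaves a weaker error statement for the secondary results. Neither needs more patients or touches the primary rules. Protocol 10.1 says that clarifications of the statistical methods are documented in the SAP, so the SAP can carry the change without a protocol amendment.

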5. STUDY DESIGN AND CONDUCT CONSIDERATIONS

5.1 Study Design

This is a multi-center, prospective, randomized, controlled, open-label, parallel study to evaluate medically stable ESRD patients receiving dialysis treatment with either the Theranova 400 dialyzer or the Elisio-17H dialyzer for 3 sessions weekly, over 24 weeks.

A sufficient number of patients will be enrolled in the study in order to randomize 166 patients in a 1:1 manner to either the Theranova 400 dialyzer or the Elisio-17H dialyzer. The study will be conducted in up to 30 study centers in the USA.

The study will have an overall duration of approximately 27 weeks per patient. This period will consist of up to 2 weeks screening period, followed by a first treatment day visit and consequent three (3) dialysis sessions per week in an in-center setting over a 24-week period, at the end of the study there will be a visit occurring on the next HD session. The assessments will be performed on monthly basis.

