5.4 Randomization Procedure

All patients who sign the ICF will be assigned a unique patient identification number. Only patients confirmed to meet screening eligibility will be randomized and allowed to continue in the study. A sufficient number of patients will be enrolled in the study in order to randomize one hundred and sixty-six (166) patients across up to thirty (30) study sites.

The type of study dialyzer each patient will use during their treatment sessions will be determined according to a central randomization scheme provided by Baxter (via the Electronic Data Capture [EDC] system used for the study). Patients will be randomly assigned to receive one of the following two study dialyzers in a 1:1 ratio:

- Theranova 400 dialyzer
- Elisio-17H dialyzer

Randomization will be stratified by site and dynamic allocation will be used.

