11.1 Primary Analysis

For the primary safety endpoint of pre-dialysis serum albumin after 24 weeks of treatment, let μ_T denote the Theranova 400 dialyzer pre-dialysis serum albumin mean and let μ_R denote the Elisio-17H dialyzer pre-dialysis serum albumin mean. Then the null hypothesis to demonstrate non-inferiority using a 5% margin can be expressed as:

Ho: μ_T - $\mu_R \leq -1.765$. The alternative hypothesis is expressed as Ha: μ_T - $\mu_R > -1.765$.

An ANCOVA model with fixed effects of treatment and site and the continuous fixed covariate of baseline pre-dialysis serum albumin will be used to generate a two-sided

95% confidence interval (CI) for the difference in treatment means (μ_T - μ_R). If the lower bound is > -1.765 then non-inferiority will be demonstrated.

The primary safety analyses will be performed using a multiple imputation approach. Multiple imputations using SAS Proc MI will be used to impute missing data under the missing at random assumption and the data sets generated will be analyzed using SAS Proc MIANALYZE (for more detail on missing data imputation see Section 7.2.2).

Twenty (20) complete data sets will be analyzed for the multiple imputation of the primary endpoint data.

The analysis of the primary safety endpoint will be carried out on both the FAS and PPS. The analysis using the PPS will be used as a supportive analysis.

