11.3 Secondary Analysis

The analysis of the secondary safety endpoints will be carried out on the FAS.

Pre-dialysis serum albumin:

A Mixed-effect Model Repeated Measurement (MMRM) model will be used to evaluate differences between treatment groups in the change from baseline in pre-dialysis serum albumin after each four weeks of treatment. The model will include the fixed effect of treatment and visit; the continuous, fixed covariate of baseline measurement; and the random effect of patient.

Pre-dialysis serum albumin will be further categorized at baseline and final measurement into 4 categories: $< 3.5, \ge 3.5-3.9, \ge 4.0-4.4, \ge 4.5$. Shift tables will be generated to cross tabulate the number of patients within each category by treatment.

Pre-dialysis Factor VII, Protein C, Vitamin A, and Factor II:

An MMRM model will be used to evaluate the differences between treatment groups in the change from baseline in pre-dialysis Factor VII, Protein C, Vitamin A, and Factor II after 4 weeks and after 24 weeks of treatment. The model will include the fixed effect of treatment, visit; the continuous, fixed covariate of baseline measurement; and the random effect of patient.

nPNA (nPCR):

An MMRM model will be used to evaluate differences between treatment groups in nPNA(nPCR) collected after each 4 weeks of treatment. The model will include the fixed effect of treatment, visit, and the random effect of patient.

AEs, SAEs, and Product Complaints:

The summary of AEs will include AEs that occur on the day of or after the first study treatment. AEs will be mapped to a Primary SOC and PT according to MedDRA and summarized descriptively by SOC, PT and treatment group. Treatment group comparability in the incidence and incidence rates of adverse events will be evaluated using Fisher's exact test and Wald's method with normal approximation, respectively.¹⁶ AEs that occur prior to 1st day of study treatment will only be listed.

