An overview (overall) summary table of all AEs will be generated that includes the total number of AEs, number and percentage of patients with at least one AE, number and percentage of patients with at least one SAE, number and percentage of patients with at least one AE probably associated with study treatment, number and percentage of patients with an AE leading to study discontinuation and number and percentage of patients with an AE leading to death. This summary table will be presented by treatment group and combining both groups (Total).

Furthermore, separate AE summary tables will be provided by SOC and PT for SAEs and AEs leading to study withdrawal. Separate AE summary tables will be provided to show a breakdown of AEs by SOC, PT and

- a. severity (mild, moderate or severe),
- a. relationship to study treatment ("probably related", "possibly related", and "unable to determine" will be categorized as "related to study treatment" while "unlikely related" and "not related" will be categorized as "unrelated to study treatment").

Study dialyzer related product complaints will be summarized descriptively by study dialyzer.

Chemistry and hematology:

Mean differences between treatment groups in the change from baseline to week 24 predialysis measure (if not applicable, end of study pre-dialysis measure will be used) in chemistry and hematology laboratory tests will be analyzed using an ANCOVA with a fixed effect of treatment and a fixed continuous covariate of baseline laboratory value. BUN will be analyzed in the change from pre-dialysis at screening to pre-dialysis after 24 weeks of treatment; further by BUN reduction ratio as compare to from screening to after 24 weeks of treatment.

The Investigator will receive the laboratory results directly from the central laboratory for review and signature. The Investigator will be notified of any laboratory value that is outside of the normal range, as defined by the laboratory. If a clinically significant change from Screening or the previous visit occurs for any laboratory value and results in medical intervention, as judged by the Investigator, the laboratory abnormality will be recorded as an AE on the eCRF. The Clinical Laboratory Evaluations eCRF page will capture and reconcile with the electronic laboratory data transfer, the sample date and time, test accession number, and if the test is an initial or re-test.

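### The secondary models omit site, although randomization is stratified by site and both primary models include it; if outcomes differ between sites, the secondary tests are conservative and lose a little power

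*SAP*

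**What the plan says.** SAP 5.4 (and protocol 5.4): "Randomization will be stratified by site and dynamic allocation will be used". SAP 5.1: "The study will be conducted in up to 30 study centers in the USA".

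Models with site:
- Primary safety, SAP 11.1: "An ANCOVA model with fixed effects of treatment and site and the continuous fixed covariate of baseline pre-dialysis serum albumin".
- Primary efficacy, SAP 12.1: "an ANCOVA model with fixed effects of treatment and site will be used".

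Models without site:
- Steps 1 to 6 and 8 of the secondary efficacy sequence, SAP 12.3: "The model will include the fixed effect of treatment, visit, and the random effect of patient".
- Step 7 (change in pre-dialysis beta-2-microglobulin), SAP 12.3: "An ANCOVA with a fixed effect of treatment and a fixed continuous effect of baseline".
- Secondary safety, albumin over time, SAP 11.3: "The model will include the fixed effect of treatment and visit; the continuous, fixed covariate of baseline measurement; and the random effect of patient". The coagulation factors and vitamin A have the same terms. The nPNA model has no baseline term and no site term.
- Chemistry and hematology, SAP 11.3: "ANCOVA with a fixed effect of treatment and a fixed continuous covariate of baseline laboratory value".
- The exploratory repeated-measures models in SAP 13 whose terms are listed.

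Protocol 10.6 has the same secondary models. SAP 7.4 pools data across sites by default. SAP 10, which lists departures from the protocol, does not mention the difference between primary and secondary models.

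**The concern.** Stratifying by site removes most of the between-site variation from the treatment comparison. A model without site leaves that variation in its error term, so it reports a standard error larger than the real one. The test then runs below its nominal 5% level.

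Some between-site variation is plausible. Protocol 5.3 and 5.7 leave dialysis prescription and management to institutional practice, and session length to the physician or investigator. Both could affect reduction ratios and Kt/V.

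Power matters most in SAP 12.3, where the eight efficacy tests form a fixed sequence and one failed step ends formal testing. The inconsistency is clearest for the lambda FLC reduction ratio: the same week-24 values enter one model with site and another without.

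**Working it through.** **The plan's own figures.** All of these reproduce.
- Albumin: margin 0.05 × 35.3 = 1.765 and SD 3.7. The normal approximation gives 2 × (1.960 + 0.842)² × 3.7² / 1.765² = 69 per group. The t-test gives 80.0% power at 70 per group.
- Dropout: 70 / 0.85 = 82.4, so 83 per group and 166 in total.
- Lambda FLC reduction ratio: a difference of 4.56 with SD 8.26 (0.55 SD) gives 90.0% power at 70 per group.

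No power is stated for any secondary test, so there is no stated figure to compare with below.

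**Standard error, ideal balance within site.** Set the total variance to 1, with a share ICC lying between sites. The model without site uses variance 1. The treatment difference actually varies with 1 − ICC. The ratio of model SE to true SE is 1/√(1 − ICC):

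| ICC (assumed) | 1/√(1 − ICC) | SE too wide by |
|---|---|---|
| 0 | 1.000 | 0% |
| 0.02 | 1.010 | 1.0% |
| 0.05 | 1.026 | 2.6% |
| 0.10 | 1.054 | 5.4% |
| 0.20 | 1.118 | 11.8% |

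At ICC 0.20 the effective critical value is 1.96 × 1.118 = 2.19, which is a two-sided level of about 2.8%.

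**Simulation with imperfect balance.** 166 patients were randomized to 30 sites, balanced in pairs within site, with 15% random dropout, two-sided 0.05 and 6,000 runs per cell. The patient mean stands in for the treatment effect of the repeated-measures model. The effect is 2.80 × √(2/70) = 0.47 SD, for about 80% power.

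| ICC | Model SE without site / true SE | Ratio | Type I error without site |
|---|---|---|---|
| 0 | 0.1682 / 0.1688 | 1.00 | 4.7% |
| 0.05 | 0.1683 / 0.1657 | 1.02 | 4.8% |
| 0.10 | 0.1679 / 0.1609 | 1.04 | 4.6% |
| 0.20 | 0.1678 / 0.1565 | 1.07 | 3.4% |

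Odd site sizes and dropout disturb the balance, so the excess is smaller than in the ideal case. The direction is the same, and the type I error is never inflated.

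**Power by model.** The same design at 30 sites, with about 140 evaluable, REML for the random intercept and 3,000 runs per cell:

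| ICC | No site | Fixed site | Random site intercept | Random minus none |
|---|---|---|---|---|
| 0 | 79.6% | 76.7% | 79.9% | 0.3 |
| 0.02 | 79.6% | 77.9% | 80.4% | 0.8 |
| 0.05 | 79.9% | 78.7% | 81.1% | 1.2 |
| 0.10 | 81.3% | 81.2% | 83.2% | 1.9 |
| 0.20 | 82.1% | 85.5% | 86.5% | 4.4 |

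Type I error with the random intercept was 4.6 to 4.8%. Without site it fell to 3.2% at ICC 0.20. A separate run of this comparison gave 80.2 / 78.7 / 80.5% at ICC 0, 80.9 / 79.9 / 81.8% at 0.05 and 83.6 / 87.2 / 88.0% at 0.20, with a type I error of 3.1% without site at 0.20.

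**Cost of fixed site effects.** Thirty sites use up to 29 degrees of freedom with 140/30 ≈ 4.7 evaluable patients per site. At ICC 0 the fixed-site SE is 0.1732 against 0.1682, or 3% wider. Fixed effects begin to narrow the SE above an ICC of about 0.06 at 30 sites, 0.03 at 20 and 0.01 at 10.

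**The case against.** The strongest reply is that nothing here threatens validity. The omission biases no estimate and inflates no type I error. Pooling across sites is the SAP's stated default (7.4), and the primary models can be read as its exceptions. With fewer than five evaluable patients per site, leaving site out can even beat fixed site effects. All of this stands, but the pooling default does not explain why the primary and secondary models differ, and a random intercept avoids the cost of fixed effects.

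The loss is also only relative. Power without site did not fall as the ICC rose; the other models gained. At the plan's own detectable difference of 0.55 SD, a simulation of the mean of two visits (assumed correlation 0.6, 30 sites) gave power without versus with fixed site of about 95 vs 94% at no site variance, and 96.5 vs 98% when site made up 20% of single-visit variance. On that assumption site would seldom decide step 1. Where the model adjusts for baseline (step 7, the change-from-baseline safety models and the laboratory ANCOVAs), baseline may absorb lasting site differences, and the figures above would overstate the effect.

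A reader might infer that the secondary standard errors are certainly too wide and that power is certainly lost. The documents do not support that, because they report no ICC, no between-site variance and no patients per site. Nor does a lost step block all secondary results: the fixed sequence covers only secondary efficacy, and the secondary safety models sit in no sequence.

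**Conclusion.** The inconsistency is real and unexplained. Its consequence is conditional and modest. If outcomes do not differ between sites, nothing is lost. Over an assumed ICC of 0 to 0.20, the secondary tests are conservative: the standard error is too wide by 0 to 12% under ideal within-site balance (about 7% at ICC 0.20 in the simulation with dropout), the type I error falls to about 3% at ICC 0.20, and about 0 to 4 power points are lost relative to a random site intercept. The blocking consequence applies only to the sequence in SAP 12.3.

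These figures assume up to 30 sites, about 140 evaluable patients, near-balance within site (the dynamic allocation algorithm is not described), random dropout and no baseline covariate. The case for acting is that the plan already randomizes by site and the better model costs essentially nothing.

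**What to change.** In SAP 12.3, add site as a random intercept to the repeated-measures models (alongside the random patient effect) and to the step 7 ANCOVA, which then becomes a linear mixed model. Do the same in SAP 11.3 and 13 for consistency. State that if the site variance is estimated as zero, the model reduces to the current one. Record the change from protocol 10.6 in SAP 10.

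The cost is a few words of SAP text and one model term, settled before database lock. In the simulations the random intercept showed no power loss at any ICC tried, including 0.

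Fixed site effects, as in the primary models, are an alternative. Their downside is about 1 to 3 power points at 30 sites if the ICC is about 0.05 or less. If the sponsor prefers to leave site out, SAP 12.3 should say so and give the reason.
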